13. STUDY MEDICATION EXPOSURE

Exposure to study medication in days will be presented by phase based on SAF.

The date of first study medication administration during DB phase will be taken from the eCRF "In-clinic dosing" form at Day 1. The date of last study medication during DB phase will be taken from the eCRF "Inclinic dosing" form at Week 6 (if subject complete the DB phase) or "End of Study Drug" form. The date of first study medication during withdrawal phase will be taken from the eCRF "Prior dose" form at Week 6. The date of last study medication during Withdrawal phase will be taken from eCRF "In-clinic dosing" form at Week 8 (if subject complete the Withdrawal phase) or "End of Study Drug" form. The date of first study medication administration during OL phase will be taken from the eCRF "In-clinic dosing" form at Week 8. The date of last study medication during Open Label phase will be taken from the eCRF "Prior dose" form at Week 54 (if subject complete the Open Label phase) or "End of Study Drug" form.

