6.1.4.2 Withdrawal Phase

The first dose of study drug of the Withdrawal Phase will be administered at Week 6/Visit 8 after removal of the ABPM device (if applicable) and the final trough vital sign measures of the DB Phase are recorded. Study drug will also be dispensed at Week 6. Subjects will return to the clinic at Week 8/Visit 9 for a vital sign assessment, a full panel of clinical laboratory tests, a physical examination, ECG, and to begin the OL Phase.

Please see [Table 9.b](#) for a full list of the procedures to be completed during the Withdrawal Phase.

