6.1.5 Open-Label Phase

Subjects will receive their first dose of OL AZM in the clinic and study drug will be dispensed at Week 8/Visit 9 after the final trough vital sign measures of the Withdrawal Phase are recorded. Each subject will also be provided with a home blood pressure monitoring (HBPM) device and a BP diary so that daily BP measures can be recorded and reviewed by the investigator during the OL Phase (see [Section 9.1.16](#)).

Instructions for drug administration during the OL Phase will be the same as during the double-blind (DB) phases; ie, study medication will be administered orally with water, at an agreed upon (by the site and subject) consistent time of day, with or without food, and will be administered in the clinic on days when a visit is scheduled.

[figure not shown]
Throughout the OL Phase, subjects will be treated to achieve and maintain a target BP of <90th percentile for age, gender, and height. For subjects with CKD, a lower BP target may be utilized at the investigator's discretion. Evidence suggesting lower BP targets are appropriate and improve renal outcomes in this patient population is summarized in [Section 6.2.6](#).

All subjects will start the OL Phase receiving AZM 10 mg which can be titrated to higher dose(s) (up to 40 mg for subjects <50 kg or up to 80 mg for subjects \geq 50 kg), and additional antihypertensive medications can be added if needed to achieve target BP. If add-on therapy is needed, the type of medication added (eg a calcium channel blocker, such as amlodipine, a diuretic, such as hydrochlorothiazide, or a beta-blocker such as metoprolol) will be determined per the investigator's clinical judgment. The recommended treatment algorithm for the OL Phase is provided in [Figure 6.b](#).

In the event that down-titration or temporary or permanent discontinuation of antihypertensive medication is indicated, dose reduction or discontinuation should begin with the additional antihypertensive drug(s) first, before the dose of AZM is reduced or discontinued. During the OL Phase subjects may continue participation in the study if AZM is temporarily discontinued for less than 2 weeks. Treatment with a dose of AZM that is above the highest dose allowed for the body weight category (ie, to 80 mg in a subject <50 kg) is not allowed.

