Assessments scheduled for Visit 9 should be completed for all subjects who are randomized and (safety permitting) for those who withdraw early from the DB Phase or Withdrawal Phase. Visit can occur within a \pm 2 day window. The following procedures will be performed:

- Vital signs (including standing measurements).
- Weight and height.
- Concomitant medications.
- AE assessment.
- Clinical laboratory tests.
- Physical exam.
- 12-lead ECG.
- Urine pregnancy test performed at the site (female subjects \geq 12 years old and younger females deemed by the investigator to be of reproductive potential).
- Pregnancy avoidance counseling (female subjects \geq 12 years old and younger females deemed by the investigator to be of reproductive potential).
- Urine alcohol drug screen (required only for subjects \geq 12 years old; may be performed for younger children if deemed appropriate by the investigator). Results must be negative for the subject to continue in the study.
- Collection of double-blind study medication and compliance assessment. If required, counsel subject or parent/legal guardian on compliance.
- IVRS/IWRS access to dispense OL study medication and register study visit (or to record early termination for subjects being terminated).
- Dispensing of OL study medication with dosing instructions.
- Administration of in-clinic first dose of OL study medication.
- Dispensing of HBPM device.
- Dispensing of BP diary.

If a subject participating in the ABPM procedure terminates early from the study and the subject (a) had a passing baseline ABPM, (b) has not been without study medication and (c) has completed at least 4 weeks of active treatment, the site should attempt to complete the early termination ABPM prior to discontinuing study medication (subject safety permitting).

For all subjects receiving study medication, the investigator must complete the End of Study eCRF page upon completion or early termination.

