13.1. DERIVATIONS

For each phase, the derivation of study medication exposure is calculated as following:

Duration of exposure (days) = date of last study medication administration in the phase – date of first study medication administration + 1.

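### SAP 13 takes three phase dose dates from records that belong to the adjacent phase, so an on-schedule completer is credited with 16 withdrawal days instead of 14 and the phases overlap

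*SAP*

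**What the plan says.** SAP 13 names an eCRF source for each phase's first and last dose:

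- **Last DB dose (completers):** the date of "last study medication during DB phase will be taken from the eCRF 'Inclinic dosing' form at Week 6".
- **First withdrawal dose:** the date of "first study medication during withdrawal phase will be taken from the eCRF 'Prior dose' form at Week 6".
- **Last withdrawal dose (completers):** the date of "last study medication during Withdrawal phase will be taken from eCRF 'In-clinic dosing' form at Week 8".
- **First open-label dose:** the date of "first study medication administration during OL phase will be taken from the eCRF 'In-clinic dosing' form at Week 8".

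Subjects who do not complete a phase take their last date from the End of Study Drug form. SAP 13.1 computes duration as last date minus first date plus 1, where the last date is the "date of last study medication administration in the phase".

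The protocol says which drug is given at the two boundary visits. At Week 6 (section 6.1.4.2): "The first dose of study drug of the Withdrawal Phase will be administered at Week 6/Visit 8", once the final trough readings of the DB Phase are recorded. At Week 8 (section 6.1.5): "Subjects will receive their first dose of OL AZM in the clinic". The Week 8 procedure list in section 9.3.5 agrees: "Administration of in-clinic first dose of OL study medication". SAP Appendix 1 likewise makes Visit 8/Week 6 the first day of withdrawal dosing and Visit 9/Week 8 the first day of open-label dosing.

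**The concern.** Set against the protocol and Appendix 1, three of the SAP 13 dates point to a dose from the neighbouring phase.

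- **(a) Last DB dose:** the Week 6 in-clinic dose is the first withdrawal dose.
- **(b) First withdrawal dose:** the dose before the Week 6 visit is normally the last DB dose.
- **(c) Last withdrawal dose:** the Week 8 in-clinic dose is the first open-label dose. SAP 13 itself uses that record as the open-label start.

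Points (a) and (b) together start the Withdrawal Phase before the DB Phase ends. The exposure tables, programmed as specified, would overstate both phases. For a child switched to placebo, the 16 counted days would include one day on the earlier active drug and one on open-label AZM.

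**Working it through.** **Inputs**

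- Day 1 is the first DB dose (SAP 6.1, Appendix 1).
- Week 6 visit = Day 43. The worked example in SAP 14.1 puts the day before Week 6 at Day 42.
- Week 8 visit = Day 43 + 14 = Day 57 (2-week Withdrawal Phase).
- Both visits have a ±2-day window (Protocol Table 9.b).
- The prior dose is taken the day before the visit. Protocol 8.2 tells families to withhold drug on visit days, and Protocol 9.1.5 has the dose before the clinic BP reading recorded in the eCRF. SAP 13 also uses the prior-dose form at Week 54 for the last open-label dose, which fits this reading.

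**The plan's own figure.** SAP 13 states no number of days. The nearest figure is the compliance example in SAP 14.1: 42 days × 3 units = 126, which reproduces. It is an accountability example and not an exposure definition, but it puts DB dosing at Days 1 to 42.

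**SAP 13 as written, on-schedule completer**

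- DB: 43 − 1 + 1 = 43 days.
- Withdrawal: 57 − 42 + 1 = 16 days.
- Sum: 59 days. DB and withdrawal overlap on Days 42 and 43; withdrawal and open-label overlap on Day 57.

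**Doses actually taken in each phase**

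- DB: 42 − 1 + 1 = 42 days, so the excess is 1/42 = 2.4%.
- Withdrawal: 56 − 43 + 1 = 14 days, so the excess is 2/14 = 14.3%.
- Sum: 56 days, with no overlap.

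**One correction at a time.** Correcting only the first withdrawal date gives 57 − 43 + 1 = 15. Correcting only the last gives 56 − 42 + 1 = 15. Both are needed to reach 14.

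**Withdrawal days in other cases**

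| Case | As written | Doses in the phase | Excess |
|---|---|---|---|
| Shortest window (Week 6 Day 45, Week 8 Day 55) | 55 − 44 + 1 = 12 | 54 − 45 + 1 = 10 | +2 (20.0%) |
| Longest window (Week 6 Day 41, Week 8 Day 59) | 59 − 40 + 1 = 20 | 58 − 41 + 1 = 18 | +2 (11.1%) |
| Dose before Week 6 missed | 57 − 41 + 1 = 17 | 56 − 43 + 1 = 14 | +3 (21.4%) |
| Dose before Week 8 missed | 57 − 42 + 1 = 16 | 55 − 43 + 1 = 13 | +3 (23.1%) |
| Home dose in error on the Week 6 visit day | 57 − 43 + 1 = 15 | 56 − 43 + 1 = 14 | +1 (7.1%) |
| Stops after 7 withdrawal days (last dose Day 49) | 49 − 42 + 1 = 8 | 49 − 43 + 1 = 7 | +1 (14.3%) |

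With dosing on the day before each visit, the completer's excess is +2 days wherever the visits fall in their windows. The DB excess is then +1 day: 1/44 = 2.3% to 1/40 = 2.5%.

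**The case against.** The best defence is that SAP Appendix 1 defines the phases visit to visit (Visit 4 to 8, 8 to 9, 9 to 16), so boundary visits are shared. On that convention, ending DB at Week 6, ending withdrawal at Week 8 and starting open-label from the same Week 8 record is consistent counting. This has some force for (a) and (c), which become a one-day boundary convention. It does not rescue (b): counting both boundary visits gives 57 − 43 + 1 = 15 days, not 16, and SAP 13 still starts withdrawal before DB ends. The convention also sits badly with SAP 13.1, which counts administrations within the phase, and with Appendix 1's own statement of when each phase's dosing begins.

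A second objection is that the content of the prior-dose form is unseen. That is fair, and (b) is an inference. Points (a) and (c) do not depend on it.

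Some stronger readings are tempting but not supported:

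- **That (b) misdates everyone who enters withdrawal.** It does not. If a home dose was taken in error on the Week 6 visit day, the prior-dose record carries the correct calendar date.
- **That the adverse event windows or the 3-day attribution rule are wrong.** SAP 16.1 defines them by the first dose of withdrawal drug and does not refer to SAP 13. Reusing the SAP 13 date would start the 3-day window one day early (Days 42–44 instead of 43–45), but the SAP does not say that it will be reused.
- **That the losartan-to-placebo switchers belong to this point.** The 3-day rule names only AZM-to-placebo switchers. That concerns event attribution in another section, and no document states a symmetric rule that it breaks. It is at most a separate minor note.

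**Conclusion.** The point stands as an error in a stated derivation rule. For an on-schedule completer SAP 13 gives 43 DB days instead of 42 and 16 withdrawal days instead of 14, with overlapping phases. If boundary visits are deliberately shared, the withdrawal figure should be 15, so the first-withdrawal date is wrong on either reading.

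The withdrawal excess is normally +2 days for completers. It is +3 if the single dose before Week 6 or before Week 8 was missed, and +1 if a home dose was taken in error on the Week 6 visit day. A non-completer who entered withdrawal normally gets +1. These sizes assume that the prior-dose form records the last dose before the visit.

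The consequence is small. Exposure is summarised descriptively, the excess should be similar across arms, and no exposure-adjusted event rate is planned. A reader might infer that the primary comparison is affected. It is not: the endpoint uses BP values at the Week 6 and Week 8 visits, and compliance in SAP 14.1 uses visit dates. Alpha and power are also unaffected. The correction is still worth making, because the tables would be wrong if programmed as specified.

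**What to change.** In SAP 13, change three source records:

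1. Last DB dose (completers): prior-dose form at Week 6.
2. First withdrawal dose: in-clinic dosing form at Week 6.
3. Last withdrawal dose (completers): prior-dose form at Week 8. Confirm that this form is collected at Week 8. SAP 13 names it only at Weeks 6 and 54, though Protocol 9.1.5 implies that it is.

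Add a programmed check that phase exposure dates do not overlap, with a rule that caps each phase's last dose date at the day before the next phase's first in-clinic dose. The cap is needed because changing the form names alone does not settle a home dose taken in error on the Week 6 visit day. There DB would end on Day 43 and withdrawal would start on Day 43, giving 43 + 14 = 57 days in a 56-day span. With the cap DB ends on Day 42 and the sum is 56.

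The cost is three form names, one check and one sentence. No new table is needed and, if the Week 8 form exists, no new data.

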13.1. DERIVATIONS

For each phase, the derivation of study medication exposure is calculated as following:

Duration of exposure (days) = date of last study medication administration in the phase – date of first study medication administration + 1.

14. STUDY MEDICATION COMPLIANCE

Compliance to study medication will be presented for the SAF.

14.1. DERIVATIONS

Compliance with study medication—based on the drug accountability data—will be calculated as the number of tablets taken (total dispensed – total returned) divided by the prescribed number of tablets

2014-000674-18 Statistical Analysis Plan Version 7.0 7.0 Document: Version Number:

Version Date:

13JAN2020

Template No.: CS_TP_BS016 Revision 5 Reference: CS_WI_BS005

Effective Date: 01Apr2018

Author:

expressed as a percentage, see calculations below. For the OL extension phase of the study, dosing is 1 tablet orally per day for study drug AZM.

For the run-in, double-blind and withdrawal phases of the study, dosing is 2 tablets and 1 capsule orally per day for the study drug and it is assumed that the subject should take medication from the visit day at which their medication is initially dispensed to their last medication return date. For example, for double-blind phase, the initial dispense date is Day 1 and the last return date is Week 6, then the subject should have taken 2 tablets and 1 capsule on Days 1 to the day before Week 6. Assuming that the day before Week 6 for the subject is Day 42, the total number of prescribed tablets would be $42 \times 3 = 126$

 Θ = Number of capsules required to be taken per day.

• "Per Visit" Compliance to study medication will be calculated as follows:

```
\frac{\{\,([N \text{ of Capsules dispensed at Visit }X(n-1)] - [N \text{ of Capsules returned at Visit }X(n)])\} \div \theta}{[\text{Date of Visit }Xn] - [\text{Date of Dispensing at Visit }Xn-1]} \times 100
```

 Compliance to study medication per phase (Visit X(n) is the last visit in the phase) will be calculated as follows:

```
  \{([N \text{ of Capsules dispensed at Visit 1}] - [N \text{ of Capsules returned at Visit 2}]) \\ + \cdots + \\ ([N \text{ of Capsules dispensed at Visit X(n-1)}] - [N \text{ of Capsules returned at Visit X(n)}])\} \div \theta \\ \hline \\ - \\ [Date \text{ of Visit X(n)}] - [Date \text{ of Dispensing at Visit 1}]
```

For subjects who permanently stop the study medication, the "Date of Visit X(n)" will be replaced by the date of study withdrawal.

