9.3.7 Follow-up (Week 54/Visit 17 or Follow-up visit after Early Termination Visit)

For subjects who complete the study, follow-up will begin the first day after the Final Visit and will continue until Week 54.

Early-terminated subjects who received study medication (single-blind placebo or active study medication) should return to the clinic approximately 2 weeks after the last dose of study medication. The visit can occur within a ± 2 -day window.

If a subject participating in the ABPM procedure terminates early from the study and the subject (a) had a passing baseline ABPM, (b) has not been without study medication and (c) has completed at least 4 weeks of active treatment, the site should attempt to complete the early termination ABPM prior to discontinuing study medication (subject safety permitting).

The following procedures will be performed for Followup (Week 54/Visit 17) or Follow-up Visit after Early Termination.

- Vital signs (including standing measurements).
- Concomitant medications.
- AE assessment.
- Urine pregnancy test performed at the site (female subjects ≥ 12 years old and younger females deemed by the investigator to be of reproductive potential).

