5.4. SAFETY ANALYSIS SET [SAF]

The safety analysis set (SAF) will contain all subjects who receive at least one dose of study medication. Subjects will be analyzed according to the study medication they received for the study phase being summarized.

If there is any uncertainty concerning a subject's treatment status, then they will be assumed treated for the purposes of analysis.

PER PROTOCOL SET [PPS] 5.5.

The per protocol analysis set (PPS) will contain all subjects in the FAS excluding those identified as major protocol violators. Major deviations from the protocol leading to exclusion from the PPS will be identified prior to database lock, but may likely include relevant entry criteria, receiving incorrect treatment assignment, taking prohibited medication, non-compliance to dosing schedule and deviation from study procedures. For the PPS major protocol violation, focus will be placed on violations that may confound the interpretation of the primary endpoint. Therefore, protocol deviations during the follow-up phase, for example, wouldn't be considered major violation for exclusion from the PPS.

7.0 Document: 2014-000674-18 Statistical Analysis Plan Version 7.0 Version Number: Author: Version Date: 13JAN2020

Template No.: CS_TP_BS016 Revision 5 Reference: CS_WI_BS005

Effective Date: 01Apr2018

Primary and Secondary efficacy analyses using the PPS will be performed.

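### For children who stop drug early, SAP 14.1 ends the compliance period at an undefined study-withdrawal date rather than the last dose, so off-drug days can count as missed doses

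*SAP*

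**What the plan says.** SAP 14.1 defines compliance as units taken (dispensed minus returned), divided by units per day, over the number of days from the first dispensing to the last visit of the phase. In the blinded phases "dosing is 2 tablets and 1 capsule orally per day for the study drug". The section gives three indications of where the period ends:

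- General assumption: "the subject should take medication from the visit day at which their medication is initially dispensed to their last medication return date".
- Formula: the date of the last visit in the phase.
- Subjects who permanently stop study medication: the last-visit date "will be replaced by the date of study withdrawal".

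Exposure is handled differently. SAP 13 states: "The date of last study medication during DB phase will be taken from the eCRF", using the in-clinic dosing form at Week 6 for those who complete the phase and the End of Study Drug form for those who do not. SAP 13.1 then counts from the first dose to the "date of last study medication administration in the phase", inclusive.

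SAP 14 says only that compliance is presented for the safety analysis set. SAP 5.5 names "non-compliance to dosing schedule" among the likely grounds for exclusion from the per-protocol set, without a numerical limit.

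**The concern.** The rule is triggered by stopping drug, but the date it uses is that of leaving the study. Between the two no dose is due, so the numerator cannot grow, while each such day adds one to the denominator. Any error from a delayed withdrawal date is therefore downward, and it falls only on children who stop early.

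Two outputs are exposed. The compliance table could show poor adherence where there was none. And if the sponsor later uses this percentage to judge dosing non-compliance for the per-protocol set, children who took every dose until they stopped could be affected by how a date was recorded.

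**Working it through.** **Inputs**

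- Units per day in the blinded phases: 2 tablets + 1 capsule = 3 (SAP 14.1).
- Denominator: closing date minus dispensing date, with no +1 (SAP 14.1 formula).
- D: days dosed, with a dose on each of Days 1 to D, so the last dose is on Day D.
- g: days from last dose to the recorded date of study withdrawal. The documents do not give it. It is an assumption, shown here at 1, 7 and 14 days.

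**Reproducing the plan's example.** SAP 14.1 states: "Assuming that the day before Week 6 for the subject is Day 42, the total number of prescribed tablets would be" 42 × 3 = 126. This reproduces. With Week 6 on Day 43, the denominator is 43 − 1 = 42 days, and full adherence scores (126/3)/42 = 100%. The formula works because the closing visit falls the day after the last dose of the phase.

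**Early stopper with full adherence**

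- Numerator: 3D/3 = D.
- Denominator: (D + g) − 1.
- Compliance = D/(D + g − 1).

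| D | g = 1 | g = 7 | g = 14 |
|---|---|---|---|
| 7 | 100% | 7/13 = 53.8% | 7/20 = 35.0% |
| 14 | 100% | 14/20 = 70.0% | 14/27 = 51.9% |
| 21 | 100% | 21/27 = 77.8% | 21/34 = 61.8% |
| 28 | 100% | 28/34 = 82.4% | 28/41 = 68.3% |

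True adherence is 100% in every cell.

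**Gap needed to fall below 70%.** D/(D + g − 1) < 0.70 when g − 1 > (3/7)D. The smallest such gap is 5 days at D=7, 8 at D=14, 11 at D=21 and 14 at D=28. The value of 70% serves only as a reference point; it is not a SAP limit for this variable.

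**Conflict with SAP 13.1.** Take a child in the DB Phase with last dose on Day 28 and withdrawal recorded on Day 42. Exposure is 28 − 1 + 1 = 28 days. The compliance denominator is 42 − 1 = 41 days, so the child scores 68.3%.

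**Testing the remedy.** If the period closes at last dose + 1 day, the denominator is (D + 1) − 1 = D, and compliance is 100% for every D and g. If it closes on the last-dose date itself, the denominator is D − 1, and D=21 gives 21/20 = 105%. The +1 is needed. For the same reason, the present rule slightly overstates compliance if withdrawal is dated on the day of the last dose (g = 0).

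**The case against.** The strongest reply is that the two dates will usually be about the same. The note to Protocol Figure 6.a asks for the Week 8 or Week 52 procedures at the time of discontinuation. Protocol 9.3.5 places drug collection, the compliance check and registration of early termination at that visit. Protocol 7.5 withdraws a child with confirmed high blood pressure on blinded treatment from the study, with no off-drug follow-up period. With withdrawal the day after the last dose, the error is nil. This stands for the orderly case. It does not settle the matter, because those procedures are requested only where possible, the SAP does not say which date it means, and SAP 13 already relies on a separate form for the end of dosing.

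Three stronger readings are tempting, and the documents do not support them.

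- *A fully adherent child below 70% would be classed as non-compliant and dropped from the per-protocol set.* SAP 14 has no cut-off and no such category. The 70% and 130% limits belong to the run-in exclusion (Protocol 7.2, criterion 6) and to a site rule on persistent non-compliance since the last visit (Protocol 9.2). SAP 5.5 gives no number.
- *The gap is typically two weeks.* Protocol 9.3.7 says that early-terminated children "should return to the clinic approximately 2 weeks after the last dose of study medication". That is a safety follow-up after the Early Termination Visit, and its procedure list has no drug return or compliance check. It does not date the withdrawal.
- *The primary result is at risk.* The primary analysis uses the full analysis set (SAP 15.1.3), which does not depend on compliance. Children who stop before Week 6 are not re-randomised, so they are outside the Withdrawal Phase analysis sets. The longer examples (D=21 or 28) cannot arise within the two-week Withdrawal Phase.

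**Conclusion.** The point holds as a minor defect of definition. SAP 14.1 closes the compliance period for early stoppers at a date that is undefined, differs from the general text of the same section, and differs from SAP 13.1. The resulting understatement is nil at a one-day gap and grows with g. It is larger for children who stop sooner: at g=7 a fully adherent child loses 30.0 points at D=14 and 17.6 points at D=28.

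These figures assume full adherence up to the last dose and a value of g that the documents do not supply. The number of children affected cannot be derived. The planning figure of 10% is total dropout over the DB and Withdrawal Phases, not the share with a delayed withdrawal date.

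The certain reach is the compliance table for the safety set. Per-protocol membership, mainly for the DB Phase secondary analyses, could be affected only if a compliance cut-off is adopted.

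**What to change.** In SAP 14.1, for subjects who permanently stop study medication, replace the date of study withdrawal with the last-dose date from the End of Study Drug form plus one day. Keep the +1, so that the denominator equals the number of days dosed and agrees with the inclusive count in SAP 13.1. Align the sentence about the last medication return date with this rule for early stoppers.

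If compliance is to inform per-protocol exclusions, state the cut-off and the period it covers in SAP 5.5 before unblinding.

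The cost is essentially one phrase in the SAP and one line of derivation code. The date is already collected, and no change to conduct or to the primary analysis is needed.
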